Study Protocol

Characteristics Predicting Clinically Relevant Reduction of Hypertension Following Adrenalectomy for Primary Aldosteronism: a Multicenter Analysis

University Medical Center Utrecht, Cancer Center,
The Netherlands
Division of Surgical Oncology and Endocrine Surgery

[name], *MSc Student*
[contact]

05-04-2016

[name], *MD PhD, [name]*
[contact]

Background

Primary aldosteronism (PA) is the excessive endogenous production of the mineralocorticoid aldosterone¹. Although various rare forms of PA exist, the vast majority of cases are accounted by either an aldosterone-producing adenoma (APA) or bilateral adrenal hyperplasia, also described as idiopathic hyperaldosteronism (IHA)^{2, 3}. During the last decades the prevalence of PA has risen, predominantly due to better awareness of disease. Several studies estimated a prevalence of PA up to 17% in an unselected population of hypertensive patients. However, in a population with resistant hypertension the reported prevalence is even higher: 17-23%. This emphasizes the clinical impact of PA on morbidity and mortality due to high blood pressure⁴⁻⁷. Since both hypertension and aldosteronism are independent risk factors for cardiovascular morbidity, the aim of treatment is curation or reduction of both⁸.

After an adrenalectomy for APA normalization of biochemical abnormalities is achieved in almost all cases. Nevertheless, curation of hypertension (SBP <140 and DBP <90 mmHg) without the need of antihypertensive medication is accomplished in only 35-45% of the cases⁹⁻¹¹. In 2008 Zarnegar *et al.* developed the Aldosteronoma Resolution Score (ARS). This score predicts the likelihood of complete resolution of the hypertension in patients with an aldosteronoma and has been validated by others⁹⁻¹¹.

Reduction of hypertension is also an important clinical outcome and is reported in 90-98% of the patients after surgery⁹⁻¹¹. In most studies reduction is defined as a certain decrease in blood pressure or antihypertensive medication. However, there is no consensus on the precise definition of reduction in these patients, which leads to incomparable results. Up until now only one study has analyzed the characteristics predicting clinically relevant reduction of hypertension¹². In a study by Worht *et al.* reduction was defined as: reduction of the number of antihypertensive drugs \geq 33% with a systolic blood pressure \leq 130mm Hg. They showed reduction in 72% of the cases (n=58). Preoperative systolic blood pressure and serum creatinine were significantly higher in patients showing no reduction of hypertension.

Objectives

Although complete resolution of hypertension is the primary goal of unilateral adrenalectomy, reduction of hypertension leads to a lifelong decrease of cardiovascular morbidity and mortality. Moreover, reduction of hypertension can lead to decrease of antihypertensive medication and thereby improve the quality of life of the patient. Therefore, reduction of hypertension is also a favorable result of adrenalectomy. The aim of the proposed study is to determine the proportion of patients with clinically relevant reduction of hypertension after adrenalectomy in a large cohort. Furthermore, we aim to determine the characteristics predicting this clinically relevant reduction. Additionally, we evaluate the predictive value of the Aldosteronoma Resolution Score for clinically relevant reduction and aim to develop a scoring system to help clinicians predict the likelihood of reduction of hypertension after adrenalectomy so it can be used for patient counseling.

Definitions/Outcome measures

To evaluate differences between those patients who were cured versus who had reduction versus who had no reduction, patients will be stratified based on clinical response to adrenalectomy. Definitions are based on both American and European guidelines for the management of hypertension^{13, 14}.

Patients who were completely off antihypertensive drugs and had a postoperative systolic blood pressure < 140 mm Hg and diastolic blood pressure < 90 mm Hg are considered as “resolution of hypertension”.

“reduction of hypertension” is defined as: a decrease in the number of antihypertensive drugs for preoperative normotensive patients (SBP < 140 and DBP < 90 mm Hg) or a decrease of postoperative blood pressure (SBP < 140 and DBP < 90 mm Hg) with the same or less number of antihypertensive drugs for patients with preoperative resistant hypertension.

Patients who are not meeting these endpoints are stratified as “no reduction of hypertension”.

Research Design

An international multicenter retrospective cohort study.

Inclusion Criteria

1. Patients with biochemical evidence of primary aldosteronism who underwent adrenalectomy on account of an aldosterone-producing adenoma (APA), proven by Computerized Tomography (CT) or Magnetic Resonance Imaging (MRI) or Adrenal Venous Sampling (AVS).
2. Operated between 2010-2016 in your institution.

Exclusion Criteria

1. Missing or incomplete data about preoperative blood pressure and number of antihypertensive drugs.
2. Missing or incomplete follow-up data about postoperative blood pressure and number of antihypertensive drugs. *We aim enter the blood pressure and number of antihypertensive drugs closest to 6 months after adrenalectomy.*

Study Variables

Patients demographics and preoperative disease characteristics will be queried, including age at time of operation, gender, history of cardiovascular events, BMI, mean preoperative systolic and diastolic blood pressure, preoperative number of antihypertensive drugs, duration of hypertension, family history of hypertension, smoking, hypercholesterolemia, diabetes and possible supplementation of potassium. The ARS will be calculated for each patient. Furthermore, results of imaging and AVS will be collected. Laboratory data collected include serum aldosterone, potassium and creatinine levels and plasma renin activity. The aldosterone to renin ratio will be calculated. Also operative characteristics (i.e., approach and tumor laterality) and pathologic diagnosis (i.e., aldosteronoma or hyperplasia and tumor size) will be reported.

Study Outcomes

The primary outcomes of this study are the postoperative mean systolic and diastolic blood pressure and the number of antihypertensive drugs. Secondary outcomes are postoperative serum aldosterone and potassium levels. Both primary and secondary outcomes will be measured at approximately 6 months after adrenalectomy (range 3-9 months).

Statistical analysis

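### The second route to reduction covers only an undefined resistant group, so other uncontrolled patients whose pressure normalises on treatment count as no reduction

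*Combined protocol and SAP*

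**What the plan says.** The Definitions/Outcome measures section sorts patients into three categories.

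- **Resolution:** "Patients who were completely off antihypertensive drugs and had a postoperative systolic blood pressure" below 140 mm Hg, with diastolic pressure below 90.
- **Reduction, first arm:** "a decrease in the number of antihypertensive drugs for preoperative normotensive patients", where normotensive means SBP below 140 and DBP below 90.
- **Reduction, second arm:** postoperative pressure below the same limits, "with the same or less number of antihypertensive drugs for patients with preoperative resistant hypertension".
- **Everyone else:** "Patients who are not meeting these endpoints are stratified as" no reduction.

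The protocol attaches no pressure threshold or drug count to the word resistant. The same section says its definitions rest on American and European guidelines, but it reproduces no definition of this term. The only other use is in the Background, which first gives the prevalence of primary aldosteronism "in an unselected population of hypertensive patients" and then says that "in a population with resistant hypertension the reported prevalence is even higher: 17-23" percent.

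The Inclusion Criteria ask for biochemical primary aldosteronism, adrenalectomy for an adenoma shown by imaging or venous sampling, and surgery in 2010-2016. They set no condition on blood pressure control or number of drugs.

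**The concern.** The two arms of reduction do not cover the cohort. The first takes patients controlled before surgery. The second takes a group whose name, in the protocol's own Background, marks a subset of hypertensive patients. Patients who were above target but not resistant belong to neither arm, and the residual rule then counts them as failures even when surgery brought them to target.

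This category is the outcome for most of the planned analysis: the proportion with reduction, the univariate tests and logistic regression, the proportion with reduction at each ARS level, and any new score meant for counselling. Responders placed among non-responders lower the proportion. They also weaken the odds ratios of predictors unrelated to resistance, and they can make any characteristic that differs between resistant and non-resistant patients look predictive through the definition alone. If resistance is judged partly by the number of drugs, the error follows preoperative drug count, which is itself a study variable.

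**Working it through.** The plan states no figure for this point, so there is none to reproduce. The check has a logical part and an illustration of size.

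**1. Coverage.** Arm 1 takes {SBP <140 and DBP <90}. Arm 2 takes {resistant}. Left out is {SBP ≥140 or DBP ≥90, and not resistant}. This set is non-empty for any meaning of resistant narrower than not normotensive, and nothing in the eligibility criteria excludes it.

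**2. Enumeration.** I applied the three definitions to every combination of preoperative control (yes/no), preoperative drugs (0-5), postoperative control (yes/no) and postoperative drugs (0-5): 2 × 6 × 2 × 6 = 144 profiles. Two readings were compared: resistant as a subset (for illustration only, uncontrolled on at least 3 drugs) and resistant as any pressure not below 140/90. Examples for patients uncontrolled before surgery and below 140/90 after it:

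| Drugs before → after | Resistant as a subset | Resistant as not normotensive |
|---|---|---|
| 2 → 0 | resolution | resolution |
| 1 → 1 | no reduction | reduction |
| 2 → 1 | no reduction | reduction |
| 2 → 2 | no reduction | reduction |
| 2 → 3 | no reduction | no reduction |
| 3 → 3 | reduction | reduction |

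Exactly three profiles differ: 1→1, 2→1 and 2→2. On the subset reading, a patient who normalises and drops from two drugs to one is a non-responder, while one who normalises on an unchanged three drugs is a responder. Another cut-off would move the boundary but not remove the gap.

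**3. Share of the cohort misplaced.** Share = g × (1 − c) × r, where
- g = share of the cohort uncontrolled but not resistant: 10-30%, assumed;
- c = share cured: 35-45%, from the Background, where cure "without the need of antihypertensive medication is accomplished in only 35-45% of the cases"; applying it to this subgroup is an assumption;
- r = share of the non-cured who reach <140/90 on the same or fewer drugs: 30-70%, assumed.

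Low: 0.10 × 0.55 × 0.30 = 0.0165. High: 0.30 × 0.65 × 0.70 = 0.1365. That is 1.7% to 13.7% of the cohort. Within the gap group, recorded reduction is 0% where it should be 0.55 × 0.30 = 16.5% to 0.65 × 0.70 = 45.5%.

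**4. Effect on odds ratios.** Here the comparison is reduction against no reduction among non-cured patients. Let h be the fraction of true responders who sit in the gap; this is a different quantity from g.
- Real predictor, assumed true reduction 60% v 42.9%: OR = (0.60/0.40)/(0.429/0.571) = 2.0. With h = 0.10 in both levels, 54.0% v 38.6% gives OR 1.87. With h = 0.30, 42.0% v 30.0% gives OR 1.69.
- Null predictor, assumed true reduction 50% in both levels, with h = 0.10 in one and 0.30 in the other: 45% v 35%, OR = (0.45/0.55)/(0.35/0.65) = 1.52.
- The same null predictor if resolution is pooled with reduction, with 40% assumed cured: 0.40 + 0.60 × 0.45 = 67% v 0.40 + 0.60 × 0.35 = 61%, OR = (0.67/0.33)/(0.61/0.39) = 1.30.

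**The case against.** The strongest reply is that the sentence sets two groups side by side, normotensive and resistant, and may have been meant as a plain split into controlled and not controlled on treatment. On that reading nobody is misclassified and only the wording is loose. The Background sentences concern prevalence in other populations and do not define this endpoint, and the cited guidelines might settle the term. This much stands: the bias depends on the narrower reading. But the broad reading is written nowhere, the protocol's only other use of the term points to a subset, and the guideline reference carries no definition into the text. Either intention requires an edit.

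The size is also mostly assumption, which is true. Only the 35-45% comes from the protocol, and it describes adrenalectomy patients overall. The odds ratios depend on where resolution patients are placed in the binary model, which the Statistical analysis section does not say; pooling them with reduction brings the spurious odds ratio down from 1.52 to about 1.30. In the dilution example the risk ratio stays at 1.40 throughout (60/42.9, 54/38.6, 42/30), so only the odds ratio shrinks.

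Finally, the primary outcomes named under Study Outcomes are postoperative blood pressure and number of drugs, which this category does not touch, and the category can be recomputed from collected data. Both points are correct. They make the repair easy, but they do not protect the reduction proportion or the analyses built on it.

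**Conclusion.** The concern holds. Followed as written, the definition scores uncontrolled, non-resistant patients who reach <140/90 on the same or fewer drugs, but at least one, as no reduction. Those who reach target off all drugs are unaffected, because they count as resolution. The undefined term and the gap follow from the text and need no numerical assumption.

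The size cannot be known from the documents. Under the stated assumptions about 2 to 14 per 100 patients are misplaced, always in the direction of too little reduction. Odds ratios can be diluted (2.0 to between 1.87 and 1.69) or created from nothing (1.52 among non-cured patients, about 1.30 if resolution is pooled with reduction). If the sponsor meant resistant as not normotensive, the misclassification disappears once that is written down. Because the category carries the stated aim and every predictor analysis, it must be corrected before the data are analysed.

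**What to change.** In the second arm, replace the reference to resistant hypertension with patients whose preoperative SBP is ≥140 or DBP is ≥90 mm Hg. This is the exact complement of the first arm, so every enrolled patient falls under one of the two. Derive the category centrally, by one rule, from the recorded pressures and drug counts before analysis. If resistance is of interest, define it and report it as a subgroup. If the narrow meaning is intended, state how uncontrolled, non-resistant patients are classified and why.

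The cost is a few words. No new data are needed: "Missing or incomplete data about preoperative blood pressure and number of antihypertensive drugs" is already an exclusion criterion, and a matching criterion covers follow-up.

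One limitation remains. The first arm still ties the category to preoperative drug count: a normotensive patient on one drug can only decrease to zero, which is resolution if pressure stays below 140/90. Associations with drug count should carry that caveat.
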